2 STUDY FLOWCHART

V1 - Screening Visit – Inclusion D0		
	Investigator	Patient information
		Inclusion and non-inclusion criteria
		Socio-demographic data
		Clinical data and scores
		Acceptance of the ISC (I-CAT)
		Concomitant bladder treatments
		Method for choosing the catheter and the patient's criteria for choosing the catheter
		Education conditions and ISC methods
		Adverse events
V2 - Follow-up visit - 3 to 12 weeks		
	Investigator	Clinical data
		Continuation of ISC
		Continued use of chosen catheter
		Concomitant bladder treatments
		Adverse events
	Patient	Daily frequency of the ISC
		Overall impression with the ISC
		Satisfaction with the catheter (on a five point scale)
		Challenges during the ISC (IC-Di-Q)
		ISC adherence (I-CAS)
V3 - End of study visit – around 6 months		
	Investigator	Clinical data
		Continuation of ISC
		Continued use of chosen catheter.
		Concomitant bladder treatments
		Adverse events
	Patient	Daily frequency of the ISC
		Overall impression with the ISC
		Satisfaction with the catheter (on a five point scale)
		Patient's final choice criteria for the catheter
		Challenges during the ISC (IC-Di-Q)
		ISC adherence (I-CAS)

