## 8 COLLECTED DATA

### Screening and inclusion visit

During this visit, the following data will be recorded in the case report form:

- Unique identifier number;
- Date of visit;
- Patient's socio-demographic data: gender, age, living alone or with someone, professional activity, level of education
- Patient's clinical data: pathology and degree of involvement, history (age of bladder issues, bladder clean out mode, urinary symptoms (USP score), concomitant bladder treatments), anorectal dysfunction (considering the impact of these disorders on vesico-sphincter balance), accessibility of urinary meatus (manual dexterity, upper limb joint range of motion, mobility, limitation of lower limb abduction in women, vision disorders, obesity, overweight with significant apron belly, prolapse in women), urethral sensitivity (normal/decreased/increased)

- Acceptance questionnaire for I-CAT ISC
- Choice of catheter: catheters presented by the nurse, catheters tried by the patient, SpeediCath (SC) catheter chosen by the patient as the first catheter for self-catheterisation and the criteria that presided over this choice
- ISC learning terms and conditions: location, duration, number of trainings in the procedure, prescription of home nursing representative
- Recommended frequency for ISC
- ISC alone or associated with spontaneous urination
- Possible adverse events
- Date of next visit

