## 9.2 Statistical analysis

The analyses will be performed using the SAS V9.4 software (or earlier version), on a frozen database, after review of data allowing to identify protocol deviations and their potential impact on the analysis criteria. Protocol deviations will be classified as minor or major. Major deviations will lead to the exclusion of patients from the per protocol (PP) population. The distribution of patients in the analysis populations will be reviewed and approved by the sponsor before the database freeze.

The description of all the parameters will be based on the type of catheter and according to the gender of the patients. Quantitative parameters will be described using the following statistics: number of non-missing data, mean, standard deviation, median, first and third quartile, minimum and maximum. Qualitative parameters will be described using the headcounts and the percentages. These will be calculated from the number of non-missing observations. In all cases, the number of missing data will be specified.

Univariate analyses then multivariate analyses by logistic regressions will be performed to identify, among the data studied (patient choice criteria at V1, his/her final choice at V3, his/her adherence to ISC, his/her satisfaction with the catheter, his/her challenges during ISC, his/her clinical and socio-demographic characteristics, etc.), the predictive factors of the final choice of the SpeediCath catheter (Standard, Compact or Flex for male patients; Standard, Compact or Compact Eve for female patients).

The same will be done for adherence to ISC at V3 (with clinical and socio-demographic characteristics at V1, I-CAT score at V1, ICDQ score at V2, type of catheter chosen).

The other secondary endpoints will be described at the different time points and according to the catheter type.

Missing data at the time of analysis will not be replaced and will be considered as such.

A statistical analysis plan will be written after approval of the protocol. This document will have a reference value for the statistical analyses.

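### The predictor list for V3 adherence omits the training, home nursing and recommended-frequency data recorded at V1

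*Protocol*

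**What the plan says.** Section 9.2 describes two sets of univariate and then multivariate logistic regressions. For the final catheter choice, the candidate list ends open: "his/her challenges during ISC, his/her clinical and socio-demographic characteristics, etc". For V3 adherence, the next paragraph names four groups and stops. It reads "The same will be done for adherence to ISC at V3 (with clinical and socio-demographic characteristics at V1, I-CAT score at V1, ICDQ score at" the second visit, and the fourth and last group is the type of catheter chosen.

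Section 8 (screening and inclusion visit) records socio-demographic data and clinical data as two bullets. The clinical bullet covers pathology, "history (age of bladder issues, bladder clean out mode, urinary symptoms (USP score), concomitant bladder treatments", anorectal dysfunction, access to the meatus and urethral sensitivity. Three further bullets stand apart from both:

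- on training and home support, "ISC learning terms and conditions: location, duration, number of trainings in the procedure, prescription of home nursing representative"
- on how often to catheterise, "Recommended frequency for ISC"
- on whether the patient also voids, "ISC alone or associated with spontaneous urination"

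The flowchart in Section 2 makes the same separation. "Education conditions and ISC methods" has its own line, apart from the lines for socio-demographic data and for clinical data and scores.

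Section 4.2 sets the objective that the regression serves: to determine which variables are associated with catheter selection and with adherence.

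**The concern.** By the protocol's own headings, learning conditions, home nursing prescription and recommended frequency belong to none of the four predictor groups. An analyst who follows 9.2 literally would fit an adherence model with no education or support variable in it.

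Two things are at stake. First, the study could not report whether training or home nursing goes with better adherence. The objective in Section 4.2 covers that question, and Sections 3 and 4 link ISC education and learning to adherence. Second, catheter type is in the model and is not randomised. Section 3 gives the nurse's advice as an example of a choice criterion, so the care team can influence the choice of catheter as well as the training. If support differs between users of different catheters and also affects adherence, the catheter coefficient absorbs part of that effect. Section 4 intends the results to guide which catheter is offered first, with better adherence as a goal, so this coefficient is likely to be used.

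**Working it through.** **1. Compare the V1 items with the adherence list.**

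| V1 item (Section 8) | Where it is recorded | Covered by the 9.2 adherence list? |
|---|---|---|
| Training location, duration, number of sessions | Own bullet | No |
| Home nursing prescription | Same bullet as training | No |
| Recommended frequency | Own bullet | No |
| ISC alone or with spontaneous urination | Own bullet | Uncertain: the bladder-emptying mode under clinical history may capture it |
| Pathology, history, dexterity, mobility, vision etc. | Clinical bullet | Yes |
| I-CAT, catheter chosen | Own bullets | Yes, named |

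**2. The plan's own figures.** The protocol gives no power, effect size or sample size for the adherence regression, so there is no directly relevant figure to reproduce. Its precision table (Section 9.1) does reproduce, using n = z²p(1−p)/w² with z² = 3.8415:

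- p = 5%, w = 2.75%: 3.8415 × 0.0475 / 0.00075625 = 241.3 (stated 241).
- p = 50%, w = 6.25%: 3.8415 × 0.25 / 0.00390625 = 245.9 (stated 246).

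These figures do not bear on the point. The only number carried forward is 250 × 0.90 = 225 patients after the 10% loss in Section 9.1. That loss is stated for the final choice criteria; applying it to adherence is an assumption.

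**3. How large could the misattribution be?** All inputs here are assumed: one binary care factor, two catheter groups of 112 (225/2, rounded down), adherence treated as yes/no, 50% adherent without the factor, and no true catheter effect.

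Let q₁ and q₀ be the share with the factor in each group, and a the adherence with the factor. Then P₁ = q₁a + (1−q₁)0.5, P₀ = q₀a + (1−q₀)0.5, and the crude OR = [P₁/(1−P₁)] / [P₀/(1−P₀)]. A factor OR of 1.5, 2 or 3 gives a = 0.60, 0.667 or 0.75.

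- Smallest unbalanced case (50% v 40%, factor OR 1.5): P₁ = 0.5×0.60 + 0.5×0.5 = 0.55; P₀ = 0.4×0.60 + 0.6×0.5 = 0.54; OR = (0.55/0.45)/(0.54/0.46) = 1.04.
- Largest case (60% v 30%, factor OR 3): P₁ = 0.6×0.75 + 0.4×0.5 = 0.65; P₀ = 0.3×0.75 + 0.7×0.5 = 0.575; OR = (0.65/0.35)/(0.575/0.425) = 1.37.

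Spurious OR, with the chance of a false p < 0.05 in brackets:

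| Share with factor | Factor OR 1.5 | Factor OR 2 | Factor OR 3 |
|---|---|---|---|
| 50% v 50% | 1.00 (5%) | 1.00 (5%) | 1.00 (5%) |
| 50% v 40% | 1.04 (5.3%) | 1.07 (5.7%) | 1.11 (6.7%) |
| 60% v 40% | 1.08 (6.0%) | 1.15 (8.0%) | 1.24 (12.1%) |
| 60% v 30% | 1.13 (7.4%) | 1.23 (11.8%) | 1.37 (21.1%) |

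The bracketed figure is Φ(d/se − 1.96) + Φ(−d/se − 1.96), with d = P₁ − P₀ and se² = [P₁(1−P₁) + P₀(1−P₀)]/112. For the last cell, d = 0.075 and se = √(0.471875/112) = 0.0649, so d/se = 1.16, which gives about 21%.

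Within each level of the factor, adherence is the same for both catheters (a with it, 0.5 without it). Adjustment therefore returns the OR to 1.00.

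**The case against.** The strongest reply is that 9.2 never says these predictors only. The closed reading rests on the missing open ending and on the contrast with the previous list. Section 9.2 also hands the reference role to an SAP that is not shown, and that SAP may widen the list. This stands as a limit: the protocol does not forbid the extra variables. It does not remove the point, because the protocol chose to name a list, and that list leaves out data the protocol itself collects for an objective it states.

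A second reply is that the study is descriptive and exploratory and claims no causal effect of catheter type. That is right, and it keeps the point modest. Even so, an objective about associated variables is poorly served by leaving out a whole group of recorded ones.

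Several stronger readings are tempting, and the documents do not support them:

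- A reader might infer that the protocol says adherence depends on training. Section 3 says only that education may not be enough to secure adherence, and it describes follow-up as monitoring compliance. That shows relevance and no more.
- A reader might infer that the omission defeats the stated hope of improving education sequences. That sentence in Section 3 concerns questions about the choice of catheter, not adherence.
- A reader might assume that care and the catheters offered differ by site. No section says so. Section 5.1 has everyone trained to current recommendations, and Section 6.2.1 requires at least two SpeediCath types to be introduced to each patient. Variation remains possible but is an assumption.
- A reader might count all four V1 items as equally omitted. Spontaneous urination may already be covered under clinical history. Recommended frequency is limited to four or more a day by eligibility, which leaves it less room to confound.

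Finally, the odds ratios above are crude. Dexterity, mobility and vision are already in the clinical group and plausibly drive home nursing prescription, so the listed covariates could remove part of any bias.

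**Conclusion.** The point holds in a limited form. As listed, the V3 adherence model contains no training, home nursing or recommended-frequency variable. It therefore cannot show whether education or support is associated with adherence, and an imbalance in these factors between catheter types could be read as a catheter association. The first part follows from the text alone. The second requires the factor to be related both to adherence and to catheter type, which the documents make plausible but do not establish.

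The documents give no size. Under the moderate assumed imbalances the spurious odds ratio is about 1.04 to 1.37, and the false-positive rate rises from 5% to between 5.3% and 21%. With no imbalance there is no bias. A reader could build a much larger figure. For example, 80% v 20% prescribed with 85% v 50% adherent gives 78% v 57% adherence and an odds ratio of 2.67. That needs a factor odds ratio of (0.85/0.15)/(0.50/0.50) = 5.67 and an extreme imbalance, and nothing in the documents supports either.

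This concerns a secondary objective. It is worth correcting, but it does not threaten the primary description of choice criteria.

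**What to change.** In Section 9.2, extend the candidate predictors of V3 adherence by one sentence:

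- Add training location, duration and number of sessions, and home nursing prescription.
- Add, as lower-priority candidates, the recommended frequency at V1, and ISC alone versus with spontaneous urination if the bladder-emptying mode under clinical history does not already capture it.
- Report the catheter-type association with adherence adjusted for these variables.

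The SAP should carry the same list and keep the number of terms proportionate to about 225 evaluable patients, for example by using a few coarse categories for the training conditions.

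The cost is one sentence and a few degrees of freedom. No new data are needed, since every item is already recorded at V1.

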- ✓ The difficulties experienced by patients during the ISC will be measured by the Intermittent Catheterisation Difficulty Questionnaire IC-Di-Q. This is a patient questionnaire validated in French, and aims to assess the difficulties encountered during the performance of the ISC. It explores in thirteen questions many factors such as pain, blockage, bleeding, spasticity, urethral sphincter spasm, in terms of frequency of occurrence and intensity. The purpose of this questionnaire is to identify the challenges faced by patients, and to follow up their progress after alternatives or solutions have been put in place (including adapting to the type of catheter).
- ✓ Patient adherence or compliance to the ISC will be measured by the Intermittent Catheterisation Adherence Scale (I-CAS). This is a patient questionnaire validated in French consisting of eight questions, seven of which have a binary answer (yes/no) and one has five proposed responses. The score ranges from 0 for strong ISC adhesion to 8 for very low adhesion.

- ✓ A study-specific self-questionnaire was also created with the support of the scientific council to determine the reasons for the patient's choice of the catheter. This questionnaire includes the patient's independent criteria (e.g. nurse's advice) and patient-specific criteria (e.g. ease of use, discretion).

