## 4 STUDY OBJECTIVES

The purpose of this exploratory study is to determine the major criteria in the choice of catheter by patients.

The results will allow for personalised counselling to be put in place for each patient, in order to offer him/her as a first-line treatment the catheter that is the most appropriate for his/her profile, with the goal of facilitating ISC learning and improving ISC adherence and acceptance.

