### 4.2 Secondary objectives

The secondary objectives are as follows:

- Document the criteria for the patient's initial choice of the SC catheter: determined by self-questionnaire at V1
- Document patient satisfaction with the SC catheter: measured on a five point scale at V2 and V3
- Document the challenges encountered during the first six months of the ISC: measured by the IC-Di-Q at V2 and V3
- Determine patient adherence to the ISC over the first six months: measured by I-CAS at V2 and V3.
- Determine the variables associated with the catheter selection and adherence to the ISC.

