**Follow-up visit at three to twelve weeks**

- Date of visit;
- Patient's clinical data. Urinary symptoms (USP score). Concomitant bladder treatments
- Self-catheterisation: methods of use, continuation of self-catheterisation, information on stopping, if applicable
- Catheter chosen: continue self-catheterisation with the chosen catheter or catheter change, information on the catheter change, if applicable
- Patient questionnaire on catheter use and satisfaction (on a five point scale),
- IC-Di-Q
- I-CAS
- Possible adverse events
- Date of next visit

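### The V3 adherence model adjusts catheter type for difficulties measured after the catheter was chosen, and no V1-adjusted model without that score is named

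*Protocol*

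**What the plan says.** Section 9.2 of the protocol first sets the procedure for the final catheter choice: "Univariate analyses then multivariate analyses by logistic regressions will be performed to identify" its predictive factors. It then applies the same procedure to ISC adherence at V3 and names the candidate variables: "with clinical and socio-demographic characteristics at V1, I-CAT score at V1, ICDQ score at V2, type of catheter chosen". ICDQ there is the questionnaire that the rest of the protocol calls IC-Di-Q. No second multivariate model is named.

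The timing comes from section 8. At inclusion the case report form records the "SpeediCath (SC) catheter chosen by the patient as the first catheter for self-catheterisation". The IC-Di-Q is not on the V1 list and first appears at the visit at 3 to 12 weeks. At that visit the form also records whether the patient has gone on to "continue self-catheterisation with the chosen catheter or catheter change".

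Section 3 says that the questionnaire "aims to assess the difficulties encountered during the performance of the ISC" and that it serves to "follow up their progress after alternatives or solutions have been put in place (including adapting to the type of catheter").

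The objective served by the model, in section 4.2, is to "Determine the variables associated with the catheter selection and adherence to the ISC". The introduction to section 4 describes the hoped-for use of the results: counselling each patient "in order to offer him/her as a first-line treatment the catheter that is the most appropriate for his/her profile", with better adherence among the goals.

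**The concern.** The order of events is: catheter chosen at V1, difficulties reported at V2, adherence measured at V3. A covariate measured after the choice, and open to influence by it, is not a baseline adjustment. With it in the model, the catheter coefficient compares users of different types who reported the same level of early difficulty. If one type is associated with better adherence partly because it causes less pain or blockage, that part is assigned to the IC-Di-Q and not to the catheter.

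There are two further consequences. If something unmeasured drives both difficulty and adherence, conditioning on difficulty can bias the catheter coefficient, even in its direction. And a V2 score does not exist when the first catheter is offered, so the full model does not match the decision that section 4 hopes to support. At stake is a report in which the only adjusted catheter result understates or misdirects what is said about first-line choice.

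**Working it through.** **No figure in the plan to reproduce.** The protocol gives no effect size for this model, and its 250 patients come from the precision of percentages (section 9.1). The check is therefore the ordering above plus an illustration. Every path value below is an assumption.

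**Illustration 1: how much is lost.** Odds ratios (OR) are for being adherent.
- Catheter type: X = 0 or 1.
- V2 difficulty: D ~ N(−0.5·X, 1), so one type lowers difficulty by 0.5 SD.
- Adherence: logit P = 0.2 − k·D + (1 − k)·0.5·X.

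The path through D contributes 0.5·k to the log-odds and the direct path 0.5·(1 − k). They sum to 0.5 for every k, so k is the mediated share. With D in the model the expected OR is exp[0.5·(1 − k)]:
- k = 0: exp(0.5) = 1.65
- k = 0.5: exp(0.25) = 1.28
- k = 0.75: exp(0.125) = 1.13
- k = 1: exp(0) = 1.00

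Simulated results (n = 400,000 for k = 0.5 to 1; the k = 0 row is the formula value, and simulation gave 1.64 for both models):

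| Mediated share k | OR without D | OR with D |
|---|---|---|
| 0 | 1.65 | 1.65 |
| 0.5 | 1.61 | 1.28 |
| 0.75 | 1.56 | 1.13 |
| 1 | 1.53 | 1.01 |

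The slow decline in the middle column reflects non-collapsibility of the odds ratio: leaving out a strong predictor pulls the OR towards 1. It does not mean that the catheter matters less.

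**Illustration 2: other structures.** ORs here are for non-adherence, so below 1 is favourable. Difficulty is shifted by −0.8 SD unless stated, and each SD of difficulty adds 1 to the log-odds. Rejection rates are from 600 replicates at N = 250.

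| Structure | OR without D | OR with D | Rejection without / with D |
|---|---|---|---|
| All through difficulty | 0.51 | 0.99 | 69% / 5% |
| Plus direct log-OR −0.4 | 0.36 | 0.67 | 96% / 23% |
| Plus direct log-OR −0.8 | 0.26 | 0.45 | 100% / 69% |
| No path through difficulty (shift 0, direct −0.8) | 0.52 | 0.45 | 70% / 76% |
| All through difficulty, plus an unmeasured shared cause | 0.54 | 1.20 | 62% / 8% |

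The last row is the distortion from shared causes: the direction reverses. The fourth row shows that adjustment does no harm when the catheter does not act through difficulty.

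**Illustration 3: whether the univariate step is enough.** Add one V1 factor that raises the log-odds of choosing the type by 0.7 per SD and lowers the log-odds of adherence by 0.7, with the whole catheter effect through difficulty. The catheter OR for adherence is 1.04 univariate, 1.50 adjusted for the V1 factor, and 0.98 once V2 difficulty is added. Only the V1-adjusted model shows the association, and it is the one that section 9.2 does not name.

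**The case against.** The strongest reply is that the objective is associational. Section 4.2 asks for associated variables in a study that calls itself exploratory and descriptive, and nothing in section 9.2 says that the model estimates an effect of catheter type. Early difficulty is a legitimate predictor of later adherence. That stands: the fault lies in reading first-line advice from the catheter coefficient, not in using the V2 score at all.

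A reader might infer more than the documents support:
- *That the model removes the route by which a catheter could affect adherence.* It removes only the part through difficulties. Sections 3 and 5.1 also mention discretion, convenience and ease of handling, and those paths stay in the coefficient. Nothing in the protocol calls difficulty the main path.
- *That the study cannot inform first-line choice, or would wrongly report no relation.* Univariate analyses and descriptions by catheter type and gender are planned, so the catheter-adherence association without the V2 score will be seen. They are unadjusted, however, and patients choose their own catheter.
- *That section 4 promises to identify the catheter that improves adherence.* It states a purpose about choice criteria and a hoped-for later use. No section says that the advice will be taken from this secondary model.

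The unseen SAP could set staged models without contradicting the protocol. That is a fair reason for moderation, but the protocol does fix the covariate list, and that list contains the post-choice score. As for dating the catheter variable, section 8 uses the chosen catheter for the V1 choice and section 9.2 uses final choice for V3, so V1 is the likelier reading. If V3 were meant, V2 difficulty could precede a switch and act partly as a confounder, and the coefficient would mean something else.

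**Conclusion.** The point holds in a limited form. The listed multivariate model gives a catheter coefficient net of early difficulties, possibly distorted by shared causes. The univariate analysis gives an unadjusted one. Neither gives the association of the V1 catheter with V3 adherence adjusted for V1 factors, which is the quantity closest to the use described in section 4.

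The size is unknown and depends on the share of the association that runs through difficulty: none is lost with no mediation, and almost all (1.53 to 1.01) only with complete mediation. These figures rest on assumed paths and show what could happen, not what will. The point concerns a secondary objective and leaves the primary one untouched. It merits a change because the remedy is cheap and uses data already collected.

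**What to change.** In section 9.2 or the SAP:
1. State that the catheter variable in the adherence model is the type chosen at V1.
2. Report a multivariate model for V3 adherence with V1 variables only (clinical and socio-demographic characteristics, I-CAT, V1 catheter type), and read the catheter-type association from it.
3. Add the IC-Di-Q at V2 in a second model, reported as the role of early difficulties in adherence. Do not read its catheter coefficient as the basis for first-line counselling.

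The cost is a sentence or two of text and one extra model to fit and report, with no new data. The small downside is that the V1-only result may be over-read. Catheters are self-selected and the IC-Di-Q has no V1 value, so residual confounding remains, and the result should be labelled an observational association and not a causal effect of catheter type.

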1 SYNOPSIS

Title	STUDY OF SPEEDICATH CATHETER SELECTION CRITERIA AT THE START OF SELF-CATHETERISATION
Short title	Eva
Sponsor	COOPLAST
Coordinator	[name]
Trial type	Multicentre observational study
Objectives	
Primary objective:          Specify the final choice criteria for the type of SpeediCath (SC) catheter that provides patient satisfaction determined by self-questionnaire at V3
 
Secondary objectives:
 
 
- Document the reasons for the patient's initial choice of the SC catheter: determined by self-questionnaire at V1
 
- Determine the patient's adherence to Intermittent Self-Catheterisation (ISC) at the end of follow-up and his/her development over the first six months: measured by I-CAS at V2 and V3
 
- Document patient satisfaction with the catheter: measured on a five point scale at V2 and V3
 
- Document challenges during the first six months of the ISC: measured by the IC-Di-Q at V2 and V3
 
- Determine the variables associated with the catheter selection and adherence to the ISC.
 

Eligibility criteria	
Inclusion criteria
 
 
• Female or male aged eighteen years or older
 
• Subject informed of the study and who decided to participate in it (non-opposition)
 
• Subject affiliated with a social security scheme or beneficiary
 
• Subject with neurogenic or non-neurogenic bladder issues, justifying the implementation of ISC to empty the bladder
 
• Subject who received his/her initial ISC training at the time of inclusion
 
• Subject for whom the expected ISC duration is at least six months
 
• Subject for whom at least two types of SC catheters have been introduced and who has chosen to use the catheters from the SpeediCath range as the first catheter for self-catheterisation
 
• Subject able to independently conduct ISC
 
• Subject for whom the healthcare professional has recommended to conduct ISC at least four times per day
 

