### 7.3 Withdrawal from the study

Enrolled patients who meet at least one of the following criteria will be withdrawn from the study:

- Participant opposed to continuing the study,
- Participant who stopped self-catheterisation.

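### The synopsis asks how I-CAS adherence develops from V2 to V3, but section 9.2 plans only per-visit description and a V3 regression, so a change in who is assessed can look like a change in adherence

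*Protocol*

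**What the plan says.** - **Objective.** The synopsis asks for adherence "at the end of follow-up and his/her development over the first six months: measured by I-CAS at V2 and V3". Section 4.2 words the same objective more weakly but names the same scale and visits: "Determine patient adherence to the ISC over the first six months: measured by I-CAS at V2 and V3".
- **Model for adherence.** After describing logistic regressions for the final choice of catheter, section 9.2 says "The same will be done for adherence to ISC at V3". That outcome sits at one visit.
- **Description.** Section 9.2 then says "The other secondary endpoints will be described at the different time points and according to the catheter type". Of the percentages for qualitative parameters it says "These will be calculated from the number of non-missing observations". Quantitative parameters are summarised with the count of non-missing values, and the number missing is always to be given.
- **Missing data.** "Missing data at the time of analysis will not be replaced and will be considered as such".
- **Withdrawal.** Section 7.3 lists among those who leave the study: "Participant who stopped self-catheterisation".
- **Scale and expected loss.** Section 3 describes I-CAS as running from 0 (strong adherence) to 8 (very low). Section 9.1 allows for 10% of enrolled patients without final choice criteria.

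**The concern.** Development between two visits is a question about the same patients at two times. Section 9.2 would answer it by setting a V2 summary beside a V3 summary, each computed on whoever has a value at that visit. The difference between them has two parts: real change in patients seen twice, and the effect of losing some V2 patients before V3. The plan gives no means of separating the two.

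The second part need not be neutral. The withdrawal rule removes patients who have stopped self-catheterisation, and it is plausible that they already had poorer I-CAS scores at V2. If so, the V3 summary looks better with nobody improving. Section 4 intends the results to feed counselling aimed at better adherence, so a reader could take that artefact as evidence that adherence improves over the first six months.

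**Working it through.** **1. The plan's own figures.** Section 9.1 works with the half-width 1.96 × √(p(1−p)/n).
- n = 250: ±2.70% at p = 5% and ±6.20% at p = 50% (stated: ±2.75% to ±6.25%).
- 10% missing, 250 × 0.9 = 225: ±2.85% and ±6.53% (stated: ±3.0% to ±6.5%).

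These agree with the protocol. They concern choice criteria, not I-CAS, and nothing below changes them. They matter here only as the source of the 10% allowance.

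**2. Share of V2 patients without V3 (L).** The 10% is of enrolled patients, so it includes losses before V2. If all of it falls after V2, L = 10%. If half falls before V2, L = 5/95 = 5.3%. A range of 5 to 10% is therefore compatible with the protocol's allowance, but it remains an assumption.

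**3. Apparent change when no patient changes.** Let patients with both visits have mean V2 score m, and let those without V3 have mean V2 score m + g. Assume everyone with V3 also has V2.
- V2 mean = (1 − L) × m + L × (m + g) = m + L × g
- V3 mean = m
- Apparent change = V3 mean − V2 mean = −L × g, an improvement if g > 0

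The documents give no value for g. Taking 1 to 3 points as an assumption, the apparent improvement in I-CAS points is:

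| L | g = 1 | g = 2 | g = 3 |
|---|---|---|---|
| 5% | 0.05 | 0.10 | 0.15 |
| 10% | 0.10 | 0.20 | 0.30 |

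An invented example: of 100 patients at V2, 90 who continue average 2 and 10 who leave average 5. The V2 mean is (90 × 2 + 10 × 5)/100 = 2.3 and the V3 mean is 2.0, an apparent gain of 0.3. The within-patient change in the 90 is 0.

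**4. As a percentage adherent.** The apparent gain is L × (share adherent among stayers − share adherent among leavers). Assume 60% of stayers are adherent and L = 10%. If 40%, 20% or 0% of leavers were adherent, the V2 figure is 58%, 56% or 54% against 60% at V3, a gain of 2, 4 or 6 percentage points. With L = 5% the gain is 1, 2 or 3 points.

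**5. With pairing.** In patients with both visits the composition term is zero by construction. What remains is the change in patients who continued.

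**The case against.** **The detail belongs in the SAP.** Section 9.2 announces an SAP and does not forbid a paired summary, so one could still be added. That is true, and it would be wrong to infer that the protocol excludes within-patient analysis. But 9.2 is not silent: it fixes description by time point, non-missing data, no replacement and a V3-only model. Followed as written, that answers the development objective poorly.

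**The sentence on the other secondary endpoints may not cover adherence**, because adherence has just been given a regression. On that reading, development is left with the general description of parameters and a V3 model, which serves it no better.

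**The objective is narrower than it looks.** Development is named only in the synopsis and only for I-CAS. This stands. A reader might extend the point to IC-Di-Q and satisfaction, but their objectives are to document values at V2 and V3, which per-visit tables do.

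**Nothing shows that leavers differ.** This also stands. A reader might infer that a false improvement is bound to appear. The withdrawal rule makes one plausible, but the protocol does not say that stoppers scored worse at V2. If they scored better, the artefact would run the other way.

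**Missing counts are reported.** They show that the denominators differ, not whether those missing at V3 had different V2 scores.

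**Precision.** A reader might add that ignoring the pairing wastes precision. Section 9.2 plans no V2-versus-V3 interval, so no planned estimate loses any.

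**Conclusion.** The concern holds for I-CAS. A stated secondary objective is met by an analysis that cannot tell a change in patients' adherence from a change in which patients are assessed. With 5 to 10% of V2 patients lacking V3 and a V2 gap of 1 to 3 points, the artefact is 0.05 to 0.3 points on a 0 to 8 scale. The gap is an assumption with no figure behind it in the protocol. The loss range is compatible with the 10% allowance but is not stated for V2 to V3, and a loss as high as 20% would have no support in the text.

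The effect is modest at the lower end, and the primary objective and sample size are untouched. The change is still worth making, because it uses data already planned and lets the report answer the question the synopsis asks.

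**What to change.** In section 9.2, add three statements:

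- The development of I-CAS is described as the within-patient change from V2 to V3, with its 95% interval, in patients with both values.
- Beside it, for patients with V2 but no V3, the report shows their V2 I-CAS and the reason V3 is missing, with stopped self-catheterisation as its own category.
- The visit-by-visit tables stay as description.

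Bring the wording of the adherence objective in section 4.2 into line with the synopsis. A paired display for IC-Di-Q, and a V2-by-V3 shift table for satisfaction, are optional.

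The cost is a few extra tables. No new visit, patient or questionnaire is needed: both I-CAS values are already planned, section 8 collects information on stopping, and sections 13.1 and 14.1 require an explanation for each missing item. Two limits should be stated with the result. It applies only to patients who continue to V3, which is why the second statement is needed. And because V2 may fall anywhere from 3 to 12 weeks, the interval over which change is measured varies between patients.
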